- 3) The benefits of activity-based interventions on exercise capacity may extend beyond the heart.¹⁷ Existing surveillance recommendations to prevent CV events focus primarily on serial measures of “cardiotoxicity”, including LV ejection fraction, and global longitudinal strain. These strategies miss the potential adverse effects of Anth-bC on peripheral arterial and skeletal muscle function. Importantly, this study will evaluate the differential effects of Anth-bC or other potentially cardiotoxic cancer therapies on components of peak VO₂.
- 4) Activity based interventions may improve cognitive function in conjunction with increases in exercise capacity during cancer treatment.⁷
- 5) NHLBI and NCI mandates: a) the NHLBI goal to improve understanding of clinical mechanisms of CV disease and thereby enable better prevention, diagnosis and treatment;²¹ and b) the NCI’s commitment to determine actionable strategies to reduce morbidity and mortality in patients with cancer.²²

However prior to submitting this application, we need to conduct a pilot open label intervention to determine the feasibility of conducting such a proposal. Our pilot will be innovative in that:

- We are developing a novel integrated, comprehensive program for promoting cardiac health and preventing CV events in NHL patients. This program addresses multiple challenges for lymphoma patients to combat exercise intolerance by enabling patients to perform both goal-

directed structured aerobic exercise and home-based physical activity after accounting for factors related to their cancer treatment (e.g., anemia, dehydration).

- The study will incorporate **new, advanced, rapid, and highly reproducible MRI combined with cardiopulmonary exercise testing (CPET) testing results to ascertain primary and secondary study aims with much smaller sample sizes than would be needed with other modalities.** Combining advanced MRI measures with the exercise variables will provide mechanistic insights into how increasing activity affects the heart versus peripheral factors associated with arteriovenous O₂ differences, impacting exercise capacity in lymphoma patients.

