The mode of activity for the center-based AE sessions will be over-ground walking and/or stationary cycling that is prescribed based on the “non-linear approach” described by Jones et al.^{34,35} This approach adheres to the principle of progressive intensity and is designed to increase exercise capacity outcomes (peak VO₂ peak and 6min walk distance), yet also permit individual “tailoring” based on each participant’s daily perceived level of fatigue and disease/treatment related symptoms. Specifically, in “non-linear” prescriptions,

Improving Exercise Capacity with a Tailored Physical Activity Intervention in Lymphoma and Breast Cancer Patients Undergoing Treatment – An addendum to NIH
R01CA167821 “Early Imaging Detection of CV Injury after Cancer”
Wake Forest Baptist Comprehensive Cancer Center
CCWFU# 99112

the AE sessions are sequenced such that the physiological “stimulus” is progressively modified with regard to the intensity and duration and in conjunction with appropriate rest and recovery sessions in order to optimize physiological adaptations. The goal for the moderate – 45-60 minute AE sessions per week is to progress the intensity from 50% to 75% of VO₂peak by the end of the 6 month progressive tailored intervention.³⁶ Strength training will initiate at similar thresholds for core and peripheral skeletal muscles in that 50% of maximal resistance exercises at 5-8 repetitions per muscle group will occur at the initial visits and then progress to 70% of maximum resistance with the same number of repetitions toward the 6 month completion of the study. The CPET will be re-assessed after 3 months of treatment to re-calculate the AE intensity level to ensure continual increase in the physiological stimulus. During AE sessions, intensity and safety will be stressed and when at the cardiac rehabilitation facilities be continuously assessed via heart rate while blood pressure at the beginning, middle, and end of each session. Participants will be encouraged to accumulate 150 minutes (~30 minutes day) of light-moderate intensity PA per week outside the program facility. Daily and weekly targets for PA will be self-monitored by the participant and validated weekly by the intervention staff from wrist-worn Fitbit and Actigraph activity monitors. Increasing lifestyle physical activity is an important supplement to the 1-2 day/wk center-based AE and provides flexibility to the participant’s schedule and disease/treatment related side effects.³⁷

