All images will be processed offline by an image analyst blinded to study group using Medis software (Leiden, Netherlands). For each slice of the cine stack obtained, pre- and post-exercise, the endocardial border of the myocardium will be contoured to determine the area of the LV blood pool at both end-systole

Improving Exercise Capacity with a Tailored Physical Activity Intervention in Lymphoma and Breast Cancer Patients Undergoing Treatment – An addendum to NIH
R01CA167821 “Early Imaging Detection of CV Injury after Cancer”
Wake Forest Baptist Comprehensive Cancer Center
CCWFU# 99112

and end-diastole. Using Simpson's rule, the areas will then be summed together and multiplied by the slice volume plus slice gap to determine LVEDV and LVESV.⁵¹ Ventricular volumes and cardiac output will be indexed to the subject's body surface area and expressed as mL/m² or L/min/m². Brachial artery blood pressure (BP) and heart rate (HR) will be recorded during volumetric image acquisition. Cardiac output will be calculated from the LV stroke volume multiplied by the HR during CMR acquisition. For quality control, A complete double reading on 15% of the CMR cases will be performed for quality control purposes. The reader variability results will be reported at 3-month intervals or if a change in personnel could affect image analysis and interpretation. Any scans with irregularities will be subjected to expert review. Like other studies conducted over the past 7 years, these images will also be used for data interpretation and for education purposes.

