Maximal (peak VO₂) and (6-minute walk) exercise capacity outcomes. In this study, measures of both maximal (peak VO₂)^{22,33,34,52-56} and sub-maximal (6-minute walk) exercise capacity will be obtained. Peak VO₂ is selected as the primary outcome measure because it is the most reproducible measures of exercise capacity and integrates the physiologic response to exercise.^{22,33,34,52-56} It provides an objective threshold of disability and a metric that forecasts adverse cardiac prognosis as well as a parameter that can be utilized to modify medical regimens to reduce the likelihood of morbidity and mortality.^{22,33,34,52-56} It is feasible in large multi-center studies, it is reproducible and standardized. It is semi-automated and is relatively inexpensive to perform. Our team of investigators has extensive experience with using peak VO₂ as a primary measure.^{22,33,34,53,54} Amongst 3 studies for which our team serves as the core lab, the reproducibility and variance of the measure in elderly individuals (>65 years old) or those with evidence of congestive HF ranges from 7% to 12% in repeated measures.^{22,33,34,52-56} We will also perform a 6-minute walk, widely used in trials of physical function interventions, measurement that is relatively easy to administer and quite feasible and provides a very accurate assessment of sub-maximal exercise capacity. Similar to peak VO₂, the 6-minute walk is an independent predictor of CV mortality. Its acquisition will allow cross comparisons of data from this cohort with other large NHLBI sponsored multi-center initiatives. Our investigative team has utilized the 6-minute walk as an outcome measure in studies of exercise interventions in individuals treated for cancer.^{57,58}

The 6-minute walk will be administered by trained study personnel using a long, enclosed corridor with a cone placed at each end of the course. Participants will be allowed to use any mobility aids they traditionally use. Participants will be instructed to walk from end to end at their own pace while attempting to cover as much ground as possible in the six minutes.

Improving Exercise Capacity with a Tailored Physical Activity Intervention in Lymphoma and Breast Cancer Patients Undergoing Treatment – An addendum to NIH
R01CA167821 “Early Imaging Detection of CV Injury after Cancer”
Wake Forest Baptist Comprehensive Cancer Center
CCWFU# 99112

Cardiopulmonary Exercise Test as part of the MRI acquisition

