After obtaining resting CMR images, the participant will perform a CPET on the treadmill following the Bruce or Modified Bruce protocol, based on current fitness level (Figure 7). Speed and grade of the treadmill will be increased gradually every three minutes until the participant reaches volitional fatigue. Throughout the CPET, ECG, rate of perceived exertion (RPE) and BP will be monitored regularly, and expired air will be collected continuously through a one-way breathing mask to determine VO₂ peak and other cardiopulmonary measures.

The metabolic system used to collect the expired gases will be calibrated, according to the manufacturer's specifications, before each test. During the CPET, a 12-lead ECG will be continuously monitored and printed at the end of each 3-minute stage. Any arrhythmias or ST-segment changes that occurred will be documented. Blood pressure and RPE will be taken during the last minute of each stage and recorded. Oxygen uptake and respiratory equivalence ratio (RER) will be monitored continuously throughout exercise. The goal for each subject will be to exceed an RER of 1.05 indicating maximal effort. Throughout the CPET, the staff will maintain constant communication with the participant to determine when the participant is at their final 30 seconds of exercise. At this point, the staff will complete a peak exercise 12-lead ECG, disconnect the electrodes, and transfer the participant to the CMR scanner. The test will be discontinued if the participant has complaints of angina or ST-segment depression >1.5 mV, or if the staff decides to terminate the test in accordance with established test termination criteria.⁵³⁻⁵⁵

Following the CPET a report is generated including a time-down report (30 second averaged) of VO₂ (ml/kg/min), VO₂ (L/min), VCO₂, METS, RER, VE, RR, FEO₂, FECO₂ and a plot for ventilatory threshold (VAT) determination. Heart rate will be determined from the ECG tracings.

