Fatigue and health-related quality of life questionnaires. The Functional Assessment of Cancer Therapy–Fatigue scale (FACT-fatigue) will be used to assess fatigue.⁵⁹ The FACT-fatigue scale is 13-item scale that has been widely used in many studies to assess cancer related fatigue. The 42-item Functional Assessment of Cancer Treatment–Lymphoma (FACT-Lym) and the 37-item FACT-B questionnaires will be used to assess disease-specific HRQOL. The FACT-Lym and FACT-B measures are composed of the FACT-General which assesses four primary HRQOL domains: physical well-being (PWB), social well-being (SWB), and emotional well-being (EWB); and an additional sub-scale that measures patient concerns related to lymphoma or breast cancer (e.g., pain, fever, swelling, fatigue, and loss of appetite). The MOS 36-item Short Form Health Survey (SF-36) will also be used as a general measure of health status. The SF-36 is perhaps the most widely used measure of health status and includes domains of vitality and physical function. A 6-item measure

of self-efficacy for exercise will be used to assess confidence in walking at a moderately fast pace for increments of 10 to 60 minutes.

Cognitive function. Based on studies of chemotherapy and cognition, cardio-function and cognition and statin therapy and cognition, we propose a battery of validated neurocognitive measures (Hopkins Verbal Learning Test-Revised, Digit Span-Backward, Controlled Oral Word Association and Trail Making Test). These tests will evaluate verbal memory, attention/concentration, working memory, language, psychomotor speed, processing speed, and executive functions, according to standardized procedures utilized currently in multiple studies by [name], including one with [name] (RO1HL118740). Additionally, key patient reported outcomes (cognitive symptoms, fatigue, mood, pain, social and physical functioning and sleep) will be assessed. Following standardized procedures used in other studies by this research team, staff will be trained in the administration of all questionnaires. Each questionnaire will be self-administered and then reviewed by a study interviewer for completeness before being uploaded into the Oncore database. A study team member will be trained to administer and scoring of all cognitive tests following standardized procedures used in other studies of cognition and cancer conducted by members of this research team.

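### Only the MRI reader is masked to arm; the effort-dependent exercise, walk and cognitive tests have neither arm masking nor separation from intervention staff, which leaves the preliminary efficacy estimates open to tester influence

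*Combined protocol and SAP*

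**What the plan says.** Section 1.0 describes the study as open label: "we need to conduct a pilot open label intervention to determine the feasibility of conducting such a proposal". The one masking statement is in Section 5.2, under MRI Variables: "All images will be processed offline by an image analyst blinded to study group using Medis software".

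The other performance outcomes in Section 5.2 are described without reference to arm:

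- **Clinic walk:** "The 6-minute walk will be administered by trained study personnel using a long, enclosed corridor".
- **CPET:** "Speed and grade of the treadmill will be increased gradually every three minutes until the participant reaches volitional fatigue", and "the staff will maintain constant communication with the participant to determine when the participant is at their final 30 seconds of exercise".
- **Cognition:** "A study team member will be trained to administer and scoring of all cognitive tests".
- **Home walk:** a spouse or partner films it, and the study team reads laps and distance from the video.

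Section 4.3 gives one CPET result a role in delivering the physical activity intervention (PAI): "The CPET will be re-assessed after 3 months of treatment to re-calculate the AE intensity level".

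Section 5.1 makes feasibility the primary outcome. Section 6.0 plans feasibility proportions, change in outcomes among PAI participants as preliminary efficacy estimates, some preliminary efficacy assessment from the Healthy Living (HLI) controls, and descriptive statistics for each measure, all to help design a future trial.

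**The concern.** The plan accepts that knowing the arm can affect a measurement, since it masks the image analyst. Contouring happens after the participant's effort is over. The outcomes in which tester and participant behaviour can move the result as it is produced are not covered.

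Participants in an exercise trial will know their arm, and open label explains that. It does not explain why testers and scorers need to know it. If PAI participants were urged on more, or scored more generously, at 3 and 6 months than at baseline, the result would look like preserved exercise capacity or cognition. Those values would then feed the effect size and variability assumed for the later trial.

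**Working it through.** No figure in the plan relates to masking, so the check sets the provisions side by side.

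| Outcome | Where tester or scorer can affect it | Safeguard in the documents | Masked to arm? |
|---|---|---|---|
| MRI volumes (5.2) | Contouring | Offline reading; 15% double reading | Yes |
| CPET peak VO2 (5.2) | Participant decides when to stop; staff are in contact throughout | Calibrated gas measurement; goal of exceeding a respiratory exchange ratio (RER) of 1.05; established termination criteria | Not stated |
| Clinic walk (5.2) | Instruction and encouragement | Trained staff; no script given | Not stated |
| Home walk (5.2, Appendix P) | Instruction; reading the video | Filmed; standard start count; pre-marked guides | Not stated |
| Trail Making (Appendix J) | Examiner must spot and point out errors while the clock runs | Fixed script; 5-minute limit | Not stated |
| COWA word fluency (Appendix J) | Prompting after silence; judging which words count | Fixed script; scoring rules; words written down | Not stated |
| HVLT-R and Digit Span (Appendix J) | Administration | Fixed script; marked for scoring at the coordinating centre | Not stated |

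**Role separation.** No text keeps a participant's interventionist from running that participant's tests. Section 5.2 mentions initial exercise testing and programme start in one sentence, as work of the same team. That makes overlap possible, not established.

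**Walk instructions.** In the clinic, participants set their own pace while trying to cover as much ground as they can. Appendix P asks for the fastest safe walk short of running. Two instructions for one outcome add variation, and more so if the share of home tests differs by arm or visit.

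**How a tester effect enters the planned estimates.** Let b0 be the tester's contribution at baseline and b1 at follow-up.

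- Observed change = true change + (b1 − b0). A constant tester effect cancels; one that shifts after assignment does not.
- If the two arms are set against each other, the bias is (b1 − b0) in PAI minus (b1 − b0) in HLI.

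The PAI change estimate can therefore be affected even without a between-arm comparison.

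**Derived measures.** By the Fick relation in Section 1.0, arteriovenous oxygen difference = VO2 / cardiac output. Masked MRI reading does not remove effort from VO2, so effort still enters this mechanistic measure.

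**Could the data expose a bias?** Section 6.0's half-widths for a mean follow t(0.975, n−1)/√n:

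- n = 12: 2.201/√12 = 0.635 SD, as stated.
- n = 15: 2.145/√15 = 0.554 SD, as stated.
- n = 8: 2.365/√8 = 0.836 SD, against 0.769 stated. That is a separate matter and does not bear on this point.
- n = 14 (planned PAI arm): 2.160/√14 = 0.577 SD.

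If someone compares 14 with 7, assuming equal SDs, SE = √(1/14 + 1/7) = 0.463 SD and the 95% half-width is 2.093 × 0.463 = 0.969 SD. These widths describe random error only. A tester effect well inside them could not be recognised from the results.

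**The case against.** The strongest reply is that this is a 21-patient, open-label feasibility pilot. Its primary outcome hardly depends on who holds the stopwatch, and its secondary objective is whether the measures can be obtained. Imprecision of the size shown above would limit the efficacy estimates in any case. All of that stands, and it limits the weight of the point.

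Safeguards also count:

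- Peak VO2 is machine-measured, and recorded RER allows effort to be checked. However, 1.05 is a goal, not a validity rule.
- The Appendix J script forbids signalling correct answers and restricts encouragement to general phrases. Its form footers have no field for arm, although they carry initials and ID.
- Home-walk distance is lap counting with little discretion.
- CPET takes place in the MRI facility, with a technologist and nurse named on the encounter form, whereas PAI sessions are held at exercise or rehabilitation centres. The text also uses different terms for interventionists and study assessors. This suggests some separation but does not require it.

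Several stronger readings are tempting but unsupported:

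- **That intervention staff will test their own participants.** The documents do not say who tests.
- **That CPET staff will urge participants on.** The stated purpose of the continuous contact is to identify the last 30 seconds before transfer to the scanner.
- **That staff have a motive to inflate the 3-month CPET.** Section 4.3 says only that it resets training intensity.
- **That a planned PAI-versus-HLI result is compromised.** Section 6.0 specifies no such estimate or test.
- **That peak VO2 is the primary endpoint at risk.** Section 5.2 uses that phrase, but Section 5.1 defines the primary outcome as feasibility.

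**Conclusion.** The gap is real and moderate. Masking is stated for the MRI reader alone. CPET, the clinic walk, and the administration and scoring of the cognitive tests have neither arm masking nor a rule separating intervention staff. The walk has the least protection, because no script is given for the clinic version. Peak VO2 and the scripted cognitive tests are better protected, though Trail Making timing and COWA judgement still depend on the examiner.

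The consequence is confined to the preliminary efficacy estimates and what the later trial builds on them. A reader might want to express it as a fraction of a standard error or of a treatment benefit. The documents give neither a tester effect nor an expected benefit in SD units, so such a percentage would be one assumption divided by another. The size is unknown. The conclusion assumes that testers can learn the arm, which is likely in an open-label exercise study, and that nothing outside these documents already separates the roles.

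**What to change.** Using current staff:

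1. Use one fixed instruction and encouragement script for CPET and one for the 6-minute walk, in both arms and at every visit. Reconcile the clinic and Appendix P walk instructions so that they ask for the same thing. Safety and stopping provisions are untouched.
2. Remove the arm label before home-walk distance is read from video and before cognitive tests are scored. COWA words are written down, so they can be scored this way. Trail Making time is fixed when recorded, so it relies on items 1 to 3 of the existing script and on the next step.
3. Where the existing roster allows, a participant's own interventionist does not run that participant's CPET, walk or cognitive tests. Report how often this was not met.
4. Report peak RER by arm and visit as a check on effort.

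The cost is protocol wording and some rostering. No new procedure or assessor is required, because item 3 is conditional on the roster. Masking will be partial, since participants may reveal their arm, and the report should say so. Masking the automated 30-second VO2 report would add little and is not requested.

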3.0 Study Population

Inclusion Criteria: We will enroll 21 eligible and consenting men and women aged 18- 85 years with non- or Hodgkin lymphoma or I-IV stage Breast Cancer patients²³⁻²⁸ that expect to receive an anthracycline based chemotherapeutic regimen or other potentially cardiotoxic cancer therapies (e.g. chemotherapy regimens [anthracyclines, trastuzumab]), immuno-therapies (immune checkpoint inhibitors [ICI's]) or radiation (within 8 weeks of completion).²⁹⁻³¹ Potential enrollees will need the capacity to walk at least 2 city blocks on a flat surface. English-speaking participants only will be enrolled. Stage IV breast cancer participants must have a 2 year survival prognosis and approval from their physician.

Exclusion criteria: The following are relative contraindications and can be considered by the medical director of the study: Uncontrolled hypertension (systolic blood pressure >190 mm Hg or diastolic blood pressure >100 mm Hg), a recent history of alcohol or drug abuse, inflammatory conditions such as lupus or inflammatory bowel disease, or another medical condition that might compromise safety or successful completion. Other exclusions include those with contraindications to MRI such as ferromagnetic cerebral aneurysm clips or other intracranial metal, pacemakers, defibrillators, functioning neurostimulator devices or other implanted electronic devices. unstable angina; inability to exercise on a treadmill or stationary cycle; significant ventricular arrhythmias (>20 PVCs/min due to gating difficulty); atrial fibrillation with uncontrolled ventricular response; acute myocardial infarction within 28 days; moving within 12 mos. of enrollment.

Rationale for selecting patient population: Patients with lymphoma or stage I-IV breast cancer were included because their disease is potentially curable and therefore late CV effects of treatment are relevant. These individuals experience rates of CV morbidity and mortality that can exceed their cancer-related mortality. We will recruit all study participants from within the Wake Forest Comprehensive Cancer Center.

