Figure 7: Upright Treadmill Exercise CMR-CPET Stress Test Protocol. (a) CMR scanner with shoulder harnesses (black arrows) to aid with correct patient/participant positioning (b) obtaining rest cine imaging; (c) placement of electrode patches and blood pressure cuff for patient monitoring; (d) treadmill exercise stressing with expired gases, and (e) repositioning the patient/participant into the scanner for post-stress cine images.

escorted into the scanner to allow researchers to collect resting CMR images (Figure 7). Upon completion, the participant then will perform a CPET, according to the Bruce or Modified Bruce protocol. When the individual indicated they were at their maximal capacity the test will be terminated and the subject will be immediately escorted quickly back into the scanner to collect immediate post exercise CMR measures. In our pilot data and in our publications, all post-exercise CMR data are initiated 20 seconds after exercise completes and acquisitions are completed within 50 seconds of leaving the treadmill. After the post exercise CMR is completed, the individual will be monitored to ensure that HR falls to <100 bpm during which recovery LV wall motion assessments will be made. All images will be acquired using the Siemens 1.5 Tesla Avanto scanner located in the Cardiovascular Imaging Center (Reynolds Tower, Wake Forest Health Sciences, Winston-Salem, North Carolina).

The CMR protocol is performed according to prior techniques⁴⁸⁻⁵⁰ & includes a series of white blood steady-state free precession cine images acquired in the short-axis plane to cover the entire left ventricle (LV) using a 5 to 10 second real-time, cardiac-gated, free breathing acquisitions with the following parameters: 6-10 slices of 8 mm thickness and 2 mm gap spanning the entire LV, a 128x72 matrix, a 340 x 255 mm field of view, 72 views per segment with view sharing, and echo spacing of 2.1 ms, resulting in a temporal resolution of 46 ms and voxel size of 2.6 x 2.6 x 8 mm. From these images, LV end-diastolic (LVEDV) and end-systolic (LVESV) volumes will be determined for calculation of the LV ejection fraction and stroke volume. Identical sets of volumetric images were acquired pre-exercise and post-exercise (<30 sec from maximal exercise stress test).

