***Please place the following information in the Patient Registration Window before the exam begins:**

- Place with the study ID number (PID) in the MRN Field.
- Place the acrostic in the Patient Name Field.
- These should be given to you by the Study Coordinator.

General Overview

This is a cardiovascular MR exam that acquires baseline imaging (pre-exercise stress test) with a peak CPET test performed in the MRI facility. Patients are escorted from the CPET test to the MRI table with auto-scanning enabled for MRI measures of post-exercise stress test beginning <20 seconds after peak exercise. Recovery LV cines are acquired after the heart rate has normalized to ensure no wall motion abnormalities were induced with stress testing.

Improving Exercise Capacity with a Tailored Physical Activity Intervention in Lymphoma and Breast Cancer Patients Undergoing Treatment – An addendum to NIH
R01CA167821 “Early Imaging Detection of CV Injury after Cancer”
Comprehensive Cancer Center of Wake Forest University (CCCWFU- #99112)

MRI Protocol – List of Sequences

BASELINE (Pre-Exercise)
Localizers

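### The only numeric ST-depression stopping limit for the maximal exercise test is printed in mV, probably a slip for mm, and as printed would practically never stop a test

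*Combined protocol and SAP*

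**What the plan says.** Section 5.2, under the heading for the cardiopulmonary exercise test, describes a treadmill test in which speed and grade rise every three minutes "until the participant reaches volitional fatigue", with a target respiratory ratio above 1.05. Three stopping routes share one sentence. The first two are symptoms and an ECG limit: "The test will be discontinued if the participant has complaints of angina or ST-segment depression >1.5 mV". The third is discretionary: "if the staff decides to terminate the test in accordance with established test termination criteria". That route cites references 53 to 55 but does not reproduce the criteria.

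The same section provides monitoring: "a 12-lead ECG will be continuously monitored and printed at the end of each 3-minute stage". It adds: "Any arrhythmias or ST-segment changes that occurred will be documented".

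The MRI text earlier in section 5.2 also describes how the test ends: "When the individual indicated they were at their maximal capacity the test will be terminated". It gives no ST limit. Nor do the MRI-CPET guideline and encounter form in Appendix C, or section 9.0 on safety monitoring.

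**The concern.** ST depression on a standard tracing is read in millimetres, and a limit of 1.5 in that unit would be an ordinary-looking stopping rule. Printed in millivolts, the same digits describe a far larger deflection. Anyone applying the sentence literally would have a numeric rule that almost no tracing could satisfy.

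The participant concerned is one who develops ST depression without chest pain, because angina stops the test by itself. The test is taken to maximal effort in people aged up to 85 who are receiving potentially cardiotoxic treatment. It is planned at study entry and at 3 and 6 months in 21 patients, so up to 21 × 3 = 63 tests. This is a participant-safety matter and has no bearing on estimation or inference.

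**Working it through.** **Inputs**

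- Printed limit: more than 1.5 mV (section 5.2, exercise test text).
- ECG gain: not stated anywhere in the documents. Assumed 10 mm/mV, with a range of 5 to 20 mm/mV.
- Intended limit: not stated. Taken as 1.5 mm on the assumption that the digits are right and the unit is wrong, with 1.0 mm and 2.0 mm as alternatives.

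The protocol gives no derivation of the limit, so there is no figure of its own to reproduce. The check is a unit conversion.

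**Step 1. The printed limit in millimetres.** Deflection in mm = mV × gain.

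| Assumed gain (mm/mV) | 1.5 mV in mm | 1.5 mm in mV |
|---|---|---|
| 5 | 1.5 × 5 = 7.5 | 1.5 / 5 = 0.30 |
| 10 | 1.5 × 10 = 15 | 1.5 / 10 = 0.15 |
| 20 | 1.5 × 20 = 30 | 1.5 / 20 = 0.075 |

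**Step 2. How far the printed limit is from a plausible intended one**, at 10 mm/mV:

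- 1.0 mm meant (0.10 mV): 1.5 / 0.10 = 15 times too high.
- 1.5 mm meant (0.15 mV): 1.5 / 0.15 = 10 times too high.
- 2.0 mm meant (0.20 mV): 1.5 / 0.20 = 7.5 times too high.

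**Step 3. The band in which the numeric trigger stays silent**, if 1.5 mm was meant: 1.5 − 0.15 = 1.35 mV, or 13.5 mm at 10 mm/mV.

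**Step 4. Whether another number fills that band.** I compared every place that bears on stopping or on cardiac risk during the test:

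| Place | What it offers | Numeric ST limit? |
|---|---|---|
| 5.2, exercise test: angina | Stops the test on symptoms | No |
| 5.2, exercise test: staff decision | Stops under cited criteria | None stated here |
| 5.2, exercise test: ECG monitoring | Continuous recording; ST changes written down | No |
| 5.2, MRI text | Stops at self-reported maximum | No |
| Appendix C, general overview | Recovery imaging for induced wall motion abnormality | No; done after the test |
| 3.0 and Appendix B | Exclusions before entry | No |

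The 1.5 mV figure therefore stands alone as the numeric ST limit.

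**The case against.** The strongest reply is that a reader might infer from the misprint that participants with painless ST depression have no protection at all. The documents do not support that. The sentence that contains the limit also allows a stop under established criteria, and staff watching a continuous 12-lead tracing can act well before 1.5 mV. Section 3.0 excludes "unstable angina; inability to exercise on a treadmill or stationary cycle", as well as significant ventricular arrhythmia and infarction within 28 days. Appendix B excludes contraindications to exercise testing. After the test, "Recovery LV cines are acquired after the heart rate has normalized to ensure no wall motion abnormalities were induced with stress testing". All of this stands, and it narrows the risk. What remains is that the discretionary route states no number in these documents, and the criteria it relies on are cited but not reproduced. The protocol also prints a figure at odds with the earlier stop that staff would presumably be expected to make.

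A second reply is that this is an obvious misprint that experienced staff would read correctly. That is likely. But the figure is a decision threshold in a rule requiring that the test be stopped, and the text does not show which figure was intended.

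A third reply is that the argument draws on knowledge outside the documents. This stands in part. The gain is assumed, and the judgement that depression of this size is practically never seen is general ECG knowledge. Varying the gain from 5 to 20 mm/mV does not rescue the printed limit, since even the lowest gives 7.5 mm.

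**Conclusion.** The concern holds for the numeric trigger. As printed, the one numeric ST limit for a maximal exercise test equals 15 mm at an assumed 10 mm/mV (7.5 to 30 mm over gains of 5 to 20 mm/mV) and would practically never stop a test. It is probably a unit slip for mm, which is an inference.

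The 10-fold size should not be read as established. It assumes that 1.5 mm was intended; with 1.0 or 2.0 mm the factor is 15 or 7.5. The documents give no frequency of painless ST depression, so no number of participants at risk can be claimed. The feasibility outcome, the sample size of 21 and the planned analysis do not depend on this limit.

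**What to change.** Correct one sentence in section 5.2. Either change the unit, so that the limit reads ST-segment depression >1.5 mm, or change the value, so that it reads >0.15 mV (1.5 mm at 10 mm/mV). Either change is enough; making both independently could introduce a new error. Stating the gain beside the figure removes the remaining ambiguity. The investigator and the medical director should confirm the intended figure before the text is changed, because the documents do not settle it.

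The cost is one unit or one value in one sentence, with no change to sample size, outcomes or analysis.
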